#### **8.3.1 Source documents**

Source documents provide evidence of the existence of the patient and substantiate the integrity of the data collected. Source documents are filed at the investigator's site.

Data entered in the eCRFs that is transcribed from source documents must be consistent with the source documents, or the discrepancies must be explained. Depending on the PMS

**Proprietary confidential information.**

© 2013 Boehringer Ingelheim International GmbH or one or more of its affiliated companies. All rights reserved.

This document may not - in full or in part - be passed on, reproduced, published or otherwise used without prior written permission.

conducting under GPSP, the investigator may need to request previous medical records or transfer records, and current medical records must be made available. For eCRFs, all of the following data must be derived from source documents:

- Patient identification (gender, date of birth, hospitalization status)
- Patient participation in the PMS (substance, patient number)
- Dates of Patient's visits, including dispensing of the medication
- Medical history (including indication and concomitant diseases, if applicable)
- Medication history
- AEs and outcome events (onset date, end date, treatment for AEs)
- Concomitant therapy (start date, changes, reasons for therapy)
- Laboratory results (in validated electronic format, if available)

### **8.3.2 Direct access to source data and documents**

The investigator / institution will permit PMS-related regulatory inspection, providing direct access to all related source data / documents. All source documents, including progress notes and copies of laboratory and medical test results, must be available at all times for inspection by health authorities (e.g. PMDA). The accuracy of the data will be verified by reviewing the documents described in [Section 8.3.1](#).

## **8.4 PROCEDURES FOR REPORTING ADVERSE EVENTS**

### **8.4.1 Time windows**

All AEs, serious and non-serious, occurring during the course of the PMS will be collected, documented and reported to the sponsor by the investigator on the appropriate CRFs. Reporting will be done according to the specific definitions and instructions detailed in the 'Adverse Event Reporting' section of the site materials (that include all necessary documents, the protocol, instructions for conducting PMS, the package insert etc.).

The investigator has the responsibility to report AEs during the specified observational phase.

Any SAE, whether or not considered related to Trazenta® Tablets, or whether or not Trazenta® Tablets has been administered, must be reported immediately via EDC system or by a NBI MR. Further details regarding this reporting procedure are provided in the site materials.

#### **8.4.2 Documentation of adverse events and patient narratives**

Expedited reporting to health authorities of SAEs, e.g. suspected expected and suspected unexpected serious adverse reactions, will be done according to J-PAL requirements. To fulfil the regulatory requirements for expedited safety reporting, the sponsor evaluates whether a particular AE is expected.

For each AE, the investigator will provide the onset, end, intensity, outcome, seriousness and action taken with Trazenta® Tablets. The investigator will determine the relationship of Trazenta® Tablets to all AEs as defined in the 'Adverse Event Reporting' section of the site materials.

#### **8.5 STATEMENT OF CONFIDENTIALITY**

Individual patient medical information obtained as a result of this PMS is considered confidential and disclosure to third parties is prohibited with the exceptions noted below. Patient confidentiality will be ensured by using patient identification code numbers.

Data generated as a result of the PMS needs to be available for inspection on request by the regulatory authorities.

#### **8.6 COMPLETION OF TRIAL**

Completion of the PMS will be notified to PMDA when the reexamination document is applied to in accordance with J-PAL and GPSP.

## 10. APPENDICES

Not applicable.

## 11 SUMMARY OF PMS STUDY PROTOCOL MODIFICATIONS

### Summary of Modifications Sheet (SOMS)

Number of Protocol modification		1
Date of Protocol modification		4 April 2013
BI Trial number		1218.95
BI Product(s)		BI 1356
Title of protocol		Post Marketing Surveillance on Long Term Drug Use of Trazenta® Tablets in Patients with type 2 Diabetes Mellitus
To be implemented only after approval of the IRB/IEC/Competent Authorities		
To be implemented immediately in order to eliminate hazard – IRB / IEC / Competent Authority to be notified of change with request for approval		
Can be implemented without IRB/IEC/ Competent Authority approval as changes involve logistical or administrative aspects only		
Section to be changed		Study sites
Description of change		The total number of study sites has been changed from 600 to 400.
Rationale for change		Since the total number of entered sites has been increased.
Section to be changed		Objectives
Description of change		To investigate the safety and efficacy of long-term daily use of Trazenta® Tablets in patients with type 2 diabetes mellitus.  has been changed to say:  To investigate the safety and efficacy of long-term daily use of Trazenta® Tablets as monotherapy in patients with type 2 diabetes mellitus.
Rationale for change		To fulfil the requirements of PMDA that

Proprietary confidential information.

© 2013 Boehringer Ingelheim International GmbH or one or more of its affiliated companies. All rights reserved.

This document may not - in full or in part - be passed on, reproduced, published or otherwise used without prior written permission.

Number of Protocol modification		1
		should perform separate surveillance without control group for the add-on therapy.
Section to be changed		No. of patients:
Description of change		Total entered: 6,000 each treatment: Trazenta ® Tablets: 3,000 Oral antidiabetic drugs except Trazenta ® Tablets: 3,000  has been changed to say:  Total entered: 3,000 each treatment: Trazenta ® Tablets: 1,500 Oral antidiabetic drugs except Trazenta ® Tablets: 1,500
Rationale for change		To fulfil the requirements of PMDA that should perform separate surveillance without control group for the add-on therapy. Originally total entered (3,000) included patients with mono therapy and add-on therapy and it was reduced as only mono therapy patients to be enrolled.
Section to be changed		2.2 STUDY OBJECTIVES
Description of change		Study objectives are to investigate the safety and efficacy of long-term daily use of Trazenta ® Tablets in patients with type 2 diabetes mellitus and.....  has been changed to say:  Study objectives are to investigate the safety and efficacy of long-term daily use of Trazenta ® Tablets as monotherapy in patients with type 2 diabetes mellitus and.....
Rationale for change		To fulfil the requirements of PMDA that should perform separate surveillance without control group for the add-on therapy.
Section to be changed		3.1 OVERALL DESIGN AND PLAN
Description of change		This PMS is a prospective study using a continuous investigation system. Patients with

Proprietary confidential information.

© 2013 Boehringer Ingelheim International GmbH or one or more of its affiliated companies. All rights reserved.

This document may not - in full or in part - be passed on, reproduced, published or otherwise used without prior written permission.

Number of Protocol modification		1
		
type 2 diabetes mellitus are included in the surveillance.
 
.....
 
Planned number of patients to be entered and have at least one observation after treatment is 3,000. Patients with type 2 diabetes mellitus who have never received Trazenta® Tablets will be enrolled in the surveillance.
 
.....
 
Planned number of patients to be entered is 3,000.
 
has been changed to say:
 
This PMS is a prospective study using a continuous investigation system. Patients with type 2 diabetes mellitus who are treated as monotherapy are included in the surveillance.
 
.....
 
Planned number of patients to be entered and have at least one observation after treatment is 1,500. Patients with type 2 diabetes mellitus who have never received Trazenta® Tablets (monotherapy) will be enrolled in the surveillance.
 
.....
 
Planned number of patients to be entered is 1,500.

Rationale for change		
To fulfil the requirements of PMDA that should perform separate surveillance without control group for the add-on therapy. Originally total entered (3,000) included patients with mono therapy and add-on therapy and it was reduced as only mono therapy patients to be enrolled.

Section to be changed		3.3 SELECTION OF POPULATION
Description of change		
Trazenta® Tablets:
 
Planned number of patients to be entered is 3,000.
 
Patients with renal dysfunction should be entered as listed below:
 
eGFR <60 mL/min/1.73m^2: 140 patients

Proprietary confidential information.

© 2013 Boehringer Ingelheim International GmbH or one or more of its affiliated companies. All rights reserved.

This document may not - in full or in part - be passed on, reproduced, published or otherwise used without prior written permission.

Number of Protocol modification		1
		
(including 40 patients with <math>\geq 15</math> mL/min/1.73m^2 and <30 mL/min/1.73m^2 and 30 patients with <15 mL/min/1.73m^2)          100 patients with hepatic dysfunction should be also entered.
 
.....
 
Other oral antidiabetic drug:          Planned number of patients to be entered is 3,000.
 
has been changed to say:
 
Trazenta® Tablets:          Planned number of patients to be entered is 1,500.          Patients with renal dysfunction should be entered as listed below:          eGFR <60 mL/min/1.73m^2: 70 patients (including 20 patients with <math>\geq 15</math> mL/min/1.73m^2 and <30 mL/min/1.73m^2 and 15 patients with <15 mL/min/1.73m^2)  50 patients with hepatic dysfunction should be also entered.
 
.....
 
Other oral antidiabetic drug:          Planned number of patients to be entered is 1,500.

Rationale for change		
To fulfil the requirements of PMDA that should perform separate surveillance without control group for the add-on therapy. Originally total entered (3,000) included patients with mono therapy and add-on therapy and it was reduced as only mono therapy patients to be enrolled.

Section to be changed		3.3.1 Inclusion criteria
Description of change		
Trazenta® Tablets: Patients with type 2 diabetes mellitus who have never been treated with Trazenta® Tablets / linagliptin before enrollment will be included.
 
has been changed to say:

Proprietary confidential information.

© 2013 Boehringer Ingelheim International GmbH or one or more of its affiliated companies. All rights reserved.

This document may not - in full or in part - be passed on, reproduced, published or otherwise used without prior written permission.

Number of Protocol modification		1
		Trazenta ® Tablets: Patients with type 2 diabetes mellitus who have never been treated with Trazenta ® Tablets / linagliptin ( monotherapy ) before enrollment will be included.
Rationale for change		To fulfil the requirements of PMDA that should perform separate surveillance without control group for the add-on therapy.
Section to be changed		7.1 STATISTICAL DESIGN - MODEL
Description of change		
This is a non-interventional, observational study to investigate the safety and efficacy of long-term use of Trazenta® Tablets in patients with type 2 diabetes mellitus.
 
has been changed to say:
 
This is a non-interventional, observational study to investigate the safety and efficacy of long-term use of Trazenta® Tablets as monotherapy in patients with type 2 diabetes mellitus.

Rationale for change		To fulfil the requirements of PMDA that should perform separate surveillance without control group for the add-on therapy.
Section to be changed		7.6 DETERMINATION OF SAMPLE SIZE
Description of change		
The sample size was determined based on the following: To detect an ADR with an incidence of 0.1% (or 0.16%) or greater in at least one patient with a probability of 95% (or 99%) or greater, at least 3,000 patients need to be entered and have at least one observation after treatment.
 
.....
 

Proprietary confidential information.

© 2013 Boehringer Ingelheim International GmbH or one or more of its affiliated companies. All rights reserved.

This document may not - in full or in part - be passed on, reproduced, published or otherwise used without prior written permission.

Number of Protocol modification		1
Rationale for change		

2. LIST OF ABBREVIATIONS

Term	Definition / description
ADR	Adverse Drug Reactions
ADS	Analysis data set
AE	Adverse event
ALT	Alanine transaminase
ASD	Absolute standard difference
AST	Aspartate transaminase
BMI	body mass index
CTP	Clinical Trial Protocol
eGFR	Estimated Glomerular Filtration Rate
EOT	End of treatment
FPG	Fasting plasma glucose
HbA _{1c}	Glycosylated haemoglobin
JDS	Japan Diabetes Society
MedDRA	Medical Dictionary for Regulatory Activities
MMRM	Mixed model repeated measures
NGSP	National Glycohemoglobin Standardization Program
PMS	post-marketing surveillance
PT	Preferred term
PV	Protocol violation
SMQ	Standardised MedDRA query
SOC	System organ class
TSAP	Trial statistical analysis plan
ULN	Upper limit of normal

3. INTRODUCTION

The purpose of this document is to provide a more technical and detailed elaboration of the principal features of the analysis described in the protocol, and to include detailed procedures for executing the statistical analysis of the post-marketing surveillance (PMS) data.

This Trial Statistical Analysis Plan (TSAP) assumes familiarity with the Clinical Trial Protocol (CTP), including Protocol Amendments. In particular, the TSAP is based on the planned analysis specification as written in CTP Section 7 “Statistical Methods and Determination of Sample Size”. Therefore, TSAP readers may consult the CTP for more background information on the study, e.g., on study objectives, study design and population, treatments, definition of measurements and variables, planning of sample size.

SAS[®] Version 9.4 will be used for all analyses.

4. CHANGES IN THE PLANNED ANALYSIS OF THE STUDY

There has been no change in the planned analysis from the statistical methods described in the CTP.

5. ENDPOINT(S)

5.1 PRIMARY ENDPOINT(S)

There is no primary endpoint for efficacy, the primary objective of the PMS study is the evaluation of safety (see the CTP Section 5.1.1).

5.2 SECONDARY ENDPOINT(S)

The secondary endpoints will be used as stated in the CTP Section 5.1.1.

5.3 FURTHER ENDPOINT(S)

The other endpoints will be used as stated in the CTP Section 5.1.1.

5.4 OTHER VARIABLE(S)

Demographic and baseline characteristics

- Sex: Male, Female
- Age [years]
Actual age based on first administration of Trazenta[®] (or other oral antidiabetic drug)
- Age categories 1: ≤50 years, 51 to 64 years, 65 to 74 years, ≥75 years
- Age categories 2: <65 years, ≥65 years
- Height [cm]
- Body weight [kg]
- Body weight categories: ≤50 kg, >50 to 70 kg, >70 to 90 kg, >90 kg
- Body mass index (BMI) [kg/m²]
 $BMI [kg/m^2] = weight [kg] / (height [m])^2$
- BMI categories 1: <25 kg/m², 25 to <30 kg/m², ≥30 kg/m²
- BMI categories 2: <25 kg/m², ≥25 kg/m²
- BMI categories 3: <30 kg/m², ≥30 kg/m²
- Waist circumference [cm]
- Renal dysfunction : estimated glomerular filtration rate (eGFR) [mL/min/1.73m²]
- eGFR categories 1: ≥90 mL/min/1.73m²(Normal), 60 to <90 mL/min/1.73m²(Mild), 30 to <60 mL/min/1.73m²(Moderate), 15 to <30 mL/min/1.73m²(Severe), <15 mL/min/1.73m² (Endstage)
- eGFR categories 2: ≥60 mL/min/1.73m², <60 mL/min/1.73m²
- Hepatic dysfunction categories 1: (>ULN [35 U/L] of AST, >ULN of ALT [35 U/L], >ULN of total bilirubin [17 umol/L], or >ULN of AL P [120 U/L]), or other
In case > ULN of AST and CK increase (>400 U/L), patients do not include in hepatic dysfunction.

Conversion factors:

$$\text{For total bilirubin: } 17.102787754404 \times [\text{mg/dL}] = [\text{umol/L}]$$

For AST, ALT, ALP: [IU/L] = [U/L]

- Hepatic dysfunction categories 2: $\leq 1*ULN$, $>1*ULN$ to $\leq 2*ULN$, $>2*ULN$ to $\leq 3*ULN$, $>3*ULN$
 - Note: worst value of AST, ALT, total bilirubin, or ALP will be used for the categorization
- Hepatic dysfunction categories 3: (Yes, No, Unknown)
 - Hepatic disorders (Narrow) (SMQ 20000005)
 - Biliary disorders (Narrow) (SMQ 20000118)
 - Note: Presence at baseline is yes
- Patient status: (In patient, Out patient)
- Indication (Type II diabetes mellitus, Other)
- Smoking status (Never, Ex-smoker, Smoker, Unknown)
- Duration of diabetes (≤ 1 years, >1 to 5 years, >5 years, Unknown)
[First administration of Trazenta[®] (or other oral antidiabetic drug) – first diagnosis of type 2 diabetes mellitus + 1 (if negative value due to the missing and imputation, then 1)] / 365.25
- Hypersensitivity factor (Yes, No, Unknown)
- Concomitant diagnosis (Yes, No, Unknown)
- Cardiovascular (SMQ) history (Yes, No, Unknown)
 - Ischemic heart disease (SMQ: 20000043)
 - Cardiac failure (SMQ: 20000004)
 - Cerebrovascular disorders (SMQ: 20000060)
 - Torsade de pointes/QT prolongation (SMQ: 20000001)
 - Note: regardless of presence at baseline
- Baseline HbA1c [%] (based on NGSP)
- Baseline HbA1c categories: $<7.0\%$, 7 to $<8\%$, 8 to $<9\%$, $\geq 9\%$
- Baseline FPG [mg/dL]
- Baseline FPG categories: <126 mg/dL, 126 to <140 mg/dL, 140 to <200 mg/dL, ≥ 200 mg/dL
- Prior antidiabetic medication at baseline (For TRZ group):[\(See Table 5.4: 1\)](#)
 - Prior antidiabetic medication at baseline 1 (Yes, No, Unknown)
 - Prior antidiabetic medication at baseline 2 (only, combination with other DM medication, none)
 - Sulfonylurea (only, combination with other DM medication, none)
 - Biguanide (only, combination with other DM medication, none)
 - Thiazolidinedione (only, combination with other DM medication, none)
 - Alpha-glucosidase inhibitor (only, combination with other DM medication, none)
 - DPP-IV inhibitor (except Linagliptin) (only, combination with other DM medication, none)
 - Glinide (only, combination with other DM medication, none)
 - SGLT2 inhibitor (only, combination with other DM medication, none)
 - Insulin (only, combination with other DM medication, none)
 - GLP-1 receptor agonist (only, combination with other DM medication, none)

- Anti-diabetic medication categories (for other OAD group): sulfonylurea, biguanide, thiazolidinedione, alpha-glucosidase inhibitor, DPP-IV inhibitor, glinide, other)

Table 5.4: 1 Categories for antidiabetic medication based on Nihon-iyakuhinshu

Class	Medication name	Code
Sulfonylurea		First 4 numbers = 3961
Biguanide		First 4 numbers = 3962
Thiazolidinedione	PIOGLITAZONE HYDROCHLORIDE	First 7 numbers = 3969007
Alpha-glucosidase inhibitor	ACARBOSE	First 7 numbers = 3969003
	VOGLIBOSE	First 7 numbers = 3969004
	MIGLITOL	First 7 numbers = 3969009
DPP-IV inhibitor	SITAGLIPTIN PHOSPHATE HYDRATE	First 7 numbers = 3969010
	VILDAGLIPTIN	First 7 numbers = 3969011
	ALOGLIPTIN BENZOATE	First 7 numbers = 3969012
	LINAGLIPTIN	First 7 numbers = 3969014
	TENELIGLIPTIN HYDROBROMIDE HYDRATE	First 7 numbers = 3969015
	ANAGLIPTIN	First 7 numbers = 3969016
	SAXAGLIPTIN HYDRATE	First 7 numbers = 3969017
	TRELAGLIPTIN SUCCINATE	First 7 numbers = 3969024
	OMARIGLIPTIN	First 7 numbers = 3969025
Glinide	NATEGLINIDE	First 7 numbers = 3969006
	MITIGLINIDE CALCIUM HYDRATE	First 7 numbers = 3969008
	REPAGLINIDE	First 7 numbers = 3969013
SGLT2 inhibitor	IPRAGLIFLOZIN	First 7 numbers = 3969018
	DAPAGLIFLOZIN	First 7 numbers = 3969019
	LUSEOGLIFLOZIN	First 7 numbers = 3969020
	TOFOGLIFLOZIN	First 7 numbers = 3969021
	CANAGLIFLOZIN	First 7 numbers = 3969022
	EMPAGLIFLOZIN	First 7 numbers = 3969023
GLP-1 receptor agonist	LIRAGLUTIDE	First 7 numbers = 2499410
	EXENATIDE	First 7 numbers = 2499411
	LIXISENATIDE	First 7 numbers = 2499415
	DULAGLUTIDE	First 7 numbers = 2499416
Insulin		First 4 numbers = 2492
Other		First 3 numbers = 396 but not above Or any combination

Treatment exposure

Duration of Trazenta[®] treatment [days] = Treatment end date – Treatment start date + 1

If a patient interrupt the Trazenta[®], such duration will not be included in the treatment exposure.

- First dose of Trazenta[®] (5mg, Other)

Pregnancy status

Pregnancy status reported at any time during the observation period: (Yes, No, Unknown)

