### 3.3 SELECTION OF POPULATION

Trazenta® Tablets:

Planned number of patients to be entered is **1,500** ~~3,000~~.

Patients with renal dysfunction should be entered as listed below:

eGFR <60 mL/min/1.73m^2: **70** ~~140~~ patients (including **20** ~~40~~ patients with ≥15 mL/min/1.73m^2 and <30 mL/min/1.73m^2 and **15** ~~30~~ patients with <15 mL/min/1.73m^2)

**50** ~~100~~ patients with hepatic dysfunction should be also entered.

Patients with hepatic dysfunction: >ULN (AST) x1 or >ULN (ALT) x1 or >ULN (Total bilirubin) x1 or >ULN (alkaline phosphatase) x1

When both AST and CK increase, patients do not include in hepatic dysfunction.

Sites throughout entire country will be equally listed according the size of the hospitals or general clinics at which Trazenta® tablets are available for prescription.

Number of patients per site is 5-10 patients. Patients will be selected by using the continuous investigation system. The continuous investigation system is commonly used in Japanese PMS and accepted as a patient selection process by the PMDA.

Continuous investigation system is a method of registration that the investigator enrolls the patients who will start administration of marketed product into the PMS continuously (without exception) until the requested number of patients is reached.

Preferably, investigators will register patients within 14 days including the day on which the administration of Trazenta® Tablets is started. However, patients who are registered over 15 days after starting administration of Trazenta® Tablets are also used for safety and efficacy analysis.

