## 7.6 DETERMINATION OF SAMPLE SIZE

The sample size was determined based on the following: To detect an ADR with an incidence of 0.20-1% (or 0.310-16%) or greater in at least one patient with a probability of 95% (or 99%) or greater, at least 1,500 3,000 patients need to be entered and have at least one observation after treatment.

[REDACTED]

Proprietary confidential information.

© 2013 Boehringer Ingelheim International GmbH or one or more of its affiliated companies. All rights reserved.

This document may not - in full or in part - be passed on, reproduced, published or otherwise used without prior written permission.

[REDACTED]

[REDACTED]

[REDACTED]

[REDACTED]

[REDACTED]

[REDACTED]

[REDACTED]

All patients within renal and hepatic dysfunction will be assessed.

If the number of patients is less than expected numbers, registration period or sample size will be extended.

Other oral antidiabetic drug:

Descriptive statistics for all baseline characteristics will be analyzed.

As this will be exploratory and descriptive and no statistical tests will be performed the same number of patients for both groups is appropriate.

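### The CK rule in SAP 5.4 removes the patient, not just the AST criterion, from hepatic dysfunction categories 1, and categories 2 has no CK rule, so the two variables disagree for the same patients

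*SAP*

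**What the plan says.** SAP 5.4 codes hepatic dysfunction in three ways. Categories 1 is an any-of-four rule that begins "Hepatic dysfunction categories 1: (>ULN [35 U/L] of AST" and continues ">ULN of ALT [35 U/L], >ULN of total bilirubin [17 umol/L], or >ULN of AL P [120 U/L"; everyone else is 'other'. The line beneath it reads "In case > ULN of AST and CK increase (>400 U/L), patients do not include in hepatic dysfunction". Its subject is the patient, and it makes no exception for a raised ALT, bilirubin or ALP.

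"Hepatic dysfunction categories 2" has four levels: up to 1, above 1 to 2, above 2 to 3, and above 3 times ULN. Its note says that the "worst value of AST, ALT, total bilirubin, or ALP will be used for the categorization". AST is among the four tests and CK is not mentioned. Categories 3 uses MedDRA queries and is not at issue here.

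The exclusion comes from protocol 3.3, which says "When both AST and CK increase, patients do not include in hepatic dysfunction". The SAP adds the 400 U/L cut-off. Protocol 3.3 also states that 50 "patients with hepatic dysfunction should be also entered", and protocol 7.6 says "All patients within renal and hepatic dysfunction will be assessed". SAP 7.1 tabulates the section 5.4 variables by treatment group with an absolute standardised difference.

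**The concern.** The exclusion is triggered by AST and CK together, but it cancels three other criteria, each of which is sufficient alone under the same definition. One more abnormal liver test can therefore move a patient out of the hepatic group. A classification meant to identify liver abnormality should not behave that way.

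The second problem is consistency. An AST value that disqualifies a patient from categories 1 can still set that patient's grade in categories 2. Both variables carry the name hepatic dysfunction and both are listed for the baseline summaries. A reader who compares the number above 1 times ULN in categories 2 with the number of hepatic patients in categories 1 would find a gap that the SAP does not explain. A programmer would also have to guess whether the CK sentence reaches categories 2 and, if so, how to grade such a patient.

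Protocol 2.1 records that the regulator asked for surveillance of patients with hepatic dysfunction, so the definition of that group should be unambiguous.

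**Working it through.** The plan gives no figure to reproduce. The check is one of logic.

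**Inputs.** Upper limits from SAP 5.4: AST 35 U/L, ALT 35 U/L, total bilirubin 17 umol/L, ALP 120 U/L; CK cut-off 400 U/L. The patient values below are illustrative assumptions.

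**Rules as worded.**
- Categories 1: 'other' if AST > 35 and CK > 400. Otherwise hepatic if any of the four tests exceeds its limit, and 'other' if none does.
- Categories 2: r = max(AST/35, ALT/35, bilirubin/17, ALP/120), placed in one of the four bands.

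**Worked patients.**

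| | AST | ALT | Bilirubin | ALP | CK | Categories 1 | r | Categories 2 |
|---|---|---|---|---|---|---|---|---|
| A | 34 | 30 | 60 | 90 | 450 | hepatic | 60/17 = 3.53 | above 3 |
| B | 40 | 30 | 60 | 90 | 450 | other | 60/17 = 3.53 | above 3 |
| C | 80 | 30 | 12 | 90 | 900 | other | 80/35 = 2.29 | above 2 to 3 |
| D | 80 | 120 | 40 | 250 | 900 | other | 120/35 = 3.43 | above 3 |

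A and B differ only in AST. B has one more abnormal test and is the one removed. In C, the AST that is set aside in categories 1 sets the grade in categories 2.

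**All patterns.** Let each of AST, ALT, bilirubin, ALP and CK be normal or raised: 2^5 = 32 patterns. Call a pattern discordant if categories 1 is 'other' while r > 1, or the reverse.
- Discordant as worded: 8 of 32, namely every pattern with raised AST and CK > 400 (2 × 2 × 2 = 8 combinations of the other three tests).
- In 7 of these 8, ALT, bilirubin or ALP is also raised. Leaving ALT out of account, bilirubin or ALP is raised in 8 − 2 = 6.
- The reverse cannot occur. A patient who is hepatic in categories 1 has at least one test above its limit, so r > 1.

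**Effect of the change.** If the CK rule voids only the AST criterion in categories 1, discordant patterns fall from 8 to 1 (raised AST alone with CK > 400, as in C). If AST is also left out of the worst value in categories 2 when CK > 400, they fall to 0. These counts let ALT still qualify. If the sponsor sets ALT aside together with AST, the change to categories 1 alone leaves 2 (bilirubin and ALP normal, ALT normal or raised), and using the same rule in both variables again gives 0.

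These are counts of possible patterns. They say nothing about how often each occurs.

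**The case against.** The strongest reply is that the rule is the study's own definition. Protocol 3.3 excludes the patient in the same way, so the SAP is not departing from the protocol, and a study may choose to leave patients with raised AST and CK out of its hepatic group. Section 5.4 also codes other characteristics in parallel, and parallel codings need not agree. The CK sentence speaks of hepatic dysfunction generally and might be meant to cover categories 2.

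It stands that this is not a SAP deviation. The rest does not remove the problem. Nothing in the visible text says why a bilirubin or ALP above its limit should stop counting because AST is also raised. If the CK sentence does cover categories 2, the worst-value note gives no grade for such a patient.

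Several stronger readings are tempting but not supported:

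- *That the adverse drug reaction comparisons are distorted.* SAP 7.8.1 refers to section 6.4 for its subgroups, and that section is redacted. Which hepatic variable is used there, if any, cannot be seen.
- *That each affected patient is a fixed share of 50.* Fifty is a recruitment target. Protocol 7.6 has all such patients assessed, so it is not the analysed denominator.
- *That a quarter of patients (8 of 32) are affected.* The patterns are not equally likely. Laboratory tests are done only if applicable, and without a CK value the rule cannot fire.
- *That the disagreement runs both ways.* It runs in one direction only.
- *That CK can explain AST and nothing else.* The documents give no rationale for the rule and do not say that CK is irrelevant to a raised ALT. The point is made here on bilirubin and ALP.

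**Conclusion.** The point holds on the wording of both documents. Any patient with AST above 35 U/L and CK above 400 U/L is 'other' in categories 1 and above 1 times ULN in categories 2, and some of these patients may qualify on bilirubin or ALP alone. No visible passage reconciles the two variables. This is more than missing detail, because the rule applied exactly as written gives the anomalous result.

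The size is modest. The number affected is not given and is probably small. The visible consequence is limited to descriptive baseline tables and their standardised differences, in a study that plans no formal inference. The conclusion assumes that the CK sentence is programmed as it reads and that the redacted section 6.4 does not change it. The correction is worth making because the hepatic group is a named population and the change is simple.

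**What to change.** In SAP 5.4, replace the CK sentence with a rule on the criterion: when AST is above ULN and CK is above 400 U/L, the AST criterion is disregarded and the remaining criteria still classify the patient. Bilirubin and ALP should clearly remain; the sponsor should state whether ALT does. Apply the same rule to the worst value in categories 2. Record the change in SAP section 4 as a clarification of protocol 3.3, since that section now reports no change from the planned analysis.

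The cost is a sentence or two in section 5.4, a small change to the derivation of both variables and the section 4 entry. No new data are needed. The change can only add patients to the categories 1 hepatic group and can only lower grades in categories 2. The downside is a small departure from the protocol's literal definition, which is why it must be recorded. The count towards the target of 50 may then differ slightly from a count made under the protocol's wording.
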